3.3 Discussion of Study Design and Choice of Control Group(s)

3.3.1 Study Design

This is an open-label, multicenter, interventional, post-marketing study in a minimum of 40 pediatric patients who need therapeutic plasma exchange (TPE). The study will be conducted at about 10-15 sites in North America.

Control Group(s)

This is an open-label study of octaplasTM to investigate its safety and tolerability in the management of pediatric patients who require TPE; there is no control group.

3.3.2 Target Parameter(s)

Safety parameters:

- Monitoring of adverse drug reactions, TEs and TEEs caused by the octaplasTM used for plasma exchange.
- Safety laboratory parameters (CBC, Chem 7, and ionized calcium).
- Investigator's assessment of overall safety.

4 STUDY POPULATION

4.1 Population Base

A minimum of 40 pediatric patients who need TPE are expected to be enrolled according to the following inclusion and exclusion criteria.

4.1.1 Inclusion Criteria

Patients who meet all of the following criteria are eligible for the study:

- 1. Patients in whom therapeutic plasma exchange is required.
- 2. Patient is male or female ≥ 2 years to ≤ 20 years of age.
- 3. Patient or patient's legal representative(s)/guardian(s) has / have given voluntarily written and signed informed consent before any study-related procedure is to be performed. If children are old enough (age usually deemed by each institution) to understand the risks and benefits of the study, they should also be informed and provide their written assent.

4.1.2 Exclusion Criteria

Patients who meet any of the following criteria are not eligible for the study:

- 1. Patient with known homozygous congenital deficiency of Protein S.
- 2. Patient has a history of severe hypersensitivity reaction to plasma-derived products or to any excipient of the investigational product.
- 3. Patient has an already known IgA deficiency with documented antibodies against IgA.
- 4. Patient is currently participating in another interventional clinical study or has participated during the past 1 month prior to study inclusion. This is not applicable to non-interventional

trials and does not exclude patients who have been exposed to Investigational Medicinal Product with a washout of at least 30 days from enrollment in LAS-213. Concurrent participation in a device study will be considered on a case by case basis.

- 5. Patient is pregnant.
- 6. Use of Angiotensin-Converting-Enzyme-inhibitors within 72 hours of the start of the first infusion episode or planned used of these medications while on study.

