Other possible adverse reactions that may occur with the use of octaplasTM are excessive bleeding caused by hyperfibrinolysis due to lower levels of plasmin inhibitor in the product, thrombosis due to lower levels of Protein S, and citrate toxicity (hypocalcemia). The infusion rate should not exceed 1 mL/kg/min. Symptoms attributable to citrate toxicity can include fatigue, paresthesia and muscle spasms, especially in patients with liver function disorders. Because octaplasTM is made from human plasma, it may carry a risk of transmitting infectious agents such as viruses and Variant Creutzfeldt-Jakob Disease. Other adverse reactions that have been reported in the post-marketing experience include hypersensitivity reactions including anaphylactoid and allergic type of reactions, alkalosis, cardiac arrest, circulatory overload, thromboembolism, tachycardia, respiratory arrest or failure, bronchospasm, pulmonary edema, dyspnea, tachypnoea, abdominal pain, vomiting, rash, erythema, fever and/or chills, chest discomfort or pain, and seroconversions (passive transfer of antibodies).

Large volumes or fast infusion rates may induce Transfusion Associated Volume Overload that is manifested by dyspnea, hypoxia, and increasing oxygen demands. Pulmonary edema can often be seen on chest X-ray. High infusion rates may rarely cause cardiovascular effects as a result of citrate toxicity (fall in ionized calcium), especially in patients with liver function disorders. octaplasTM should be used with caution in patients with risks for thrombotic complications because of the potential for increased risk of venous thromboembolism. In order to reduce the risk for venous thromboembolism, appropriate measures should be considered in all patients at risk for thrombotic complications subjected to coagulation factor support for an extended period of time (e.g., during long-term, large-volume Therapeutic Plasma Exchange) using octaplasTM.

Administration of octaplasTM must be based on ABO-blood group compatibility with the recipient. Hemolytic reactions can occur with ABO blood group mismatches. In emergency cases blood group AB can be regarded as the universal plasma since it can be given to all patients.

octaplasTM should not be used in patients with:

- Immunoglobulin A (IgA) deficiency
- Severe deficiency of Protein S
- History of hypersensitivity to FFP or to plasma-derived products including any plasma protein
- History of hypersensitivity reaction to octaplasTM

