4 CONTRAINDICATIONS

Do not use Octaplas in patients with:

- IgA deficiency
- Severe deficiency of Protein S
- History of hypersensitivity to fresh frozen plasma (FFP) or to plasma-derived products including any plasma protein
- History of hypersensitivity reaction to Octaplas

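### Exclusions 2 and 3 are narrower than the protocol's own contraindications, so a child in whom the product is contraindicated can meet the entry criteria

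*Protocol*

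**What the plan says.** Three of the six exclusion criteria in Protocol section 4.1.2, repeated in the synopsis, deal with known risks of the product:

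- Exclusion 1: "Patient with known homozygous congenital deficiency of Protein S".
- Exclusion 2: "Patient has a history of severe hypersensitivity reaction to plasma-derived products or to any excipient of the investigational product".
- Exclusion 3: "Patient has an already known IgA deficiency with documented antibodies against IgA".

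The Benefit-Risk Statement (section 1.3) ends with a list of patients in whom the product should not be used. It includes "Immunoglobulin A (IgA) deficiency" and "History of hypersensitivity to FFP or to plasma-derived products including any plasma protein", together with severe Protein S deficiency and past hypersensitivity to the product itself. Section 4 of the package insert in Appendix 1 gives the same four items as contraindications, among them "Severe deficiency of Protein S", "History of hypersensitivity to fresh frozen plasma (FFP) or to plasma-derived products including any plasma protein" and "History of hypersensitivity reaction to Octaplas".

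Sections 5.5 and 5.7.1 say that the product is used according to its approved labeling and dispensed in line with the package insert. Section 4.4 says that every enrolled patient will be treated with octaplas.

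**The concern.** The entry criteria and the contraindications sit in one protocol and do not match. Someone who checks a child against section 4.1.2 can find the child eligible, while someone who checks the same child against section 1.3 or the insert finds that the product should be withheld. Sites could reach opposite decisions.

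If section 4.1.2 alone guides the decision, a child may receive a product that the protocol advises against for that child. The protocol treats the underlying risks as real: section 1.3 lists anaphylactic shock among the serious reactions seen, and section 8.4 of the insert says that safety in pediatric patients has not been evaluated.

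There is also a record-keeping consequence. Such an enrollment would not breach the entry criteria, so it would not fall under that example of a deviation in Protocol section 4.5 or in the per-protocol definition in SAP section 7. Both lists are open, so an infusion against the labeling could still be recorded as another kind of deviation.

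**Working it through.** No arithmetic applies. The check sets each contraindication beside the matching exclusion, then looks for other text that closes the gap.

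| Contraindication (1.3; insert section 4) | Matching exclusion (4.1.2) | Limiting phrase added | Child who can enter |
|---|---|---|---|
| IgA deficiency, unqualified | No. 3 | documented anti-IgA antibodies | Known IgA deficiency, antibodies absent or never tested |
| Hypersensitivity to FFP or plasma-derived products, any grade | No. 2 | severe | Past mild or moderate reaction |
| Hypersensitivity to octaplas, any grade | No. 2 | severe | Past mild or moderate reaction |
| Severe Protein S deficiency | No. 1 | homozygous congenital | Severe deficiency of another kind, if any is counted as severe |

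**Conventions.** FFP and octaplas are taken to fall under the plasma-derived products of exclusion 2, which is the reading most favorable to the protocol. The word *known* is not counted as a narrowing, since a site can act only on what is known. Exclusion 2 is wider than the contraindications in one respect, because it covers any excipient, but that does not close the severity gap.

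**Count.** Two of the six exclusions (nos. 2 and 3) are clearly narrower. Between them they leave three of the four contraindications only partly covered, although two of those three rows turn on the same word, *severe*. The fourth row is uncertain: neither section 1.3 nor the insert defines *severe* for Protein S, so the gap beyond homozygous congenital deficiency may be small or nil.

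**Does anything else close the gap?**

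1. Inclusion criteria (4.1.1): none requires that contraindications be absent.
2. Screening (3.2.1, 6.1.1, 7.3.5): no IgA, anti-IgA or Protein S test. Medical history may reveal a known deficiency or past reaction, but section 4.1.2 then decides whether it excludes.
3. Labeling and dispensing (5.5, 5.7.1): these govern use of the product, not entry.
4. Withdrawal (4.3.1): the investigator may withdraw a patient in that patient's interest. This is a judgment in each case and does not define eligibility.
5. Stated reason: none was found for the narrowing. Section 4.2.2, by contrast, explains the ACE-inhibitor restriction by the risk of hypotension.

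**The case against.** The strongest reply is that a site is bound by the whole protocol. Eligibility permits enrollment but does not compel it, and a site can satisfy every section by not using octaplas in a contraindicated child. Sections 1.3, 5.5 and 5.7.1 all point that way. This stands as far as it goes: the documents do not show that any contraindicated child will be infused. It does not remove the mismatch. Sections 5.5 and 5.7.1 act only at the point of use, and section 4.4 plans treatment for everyone enrolled. Nor can the labeling statement import every limit of the insert, whose plasma-exchange indication is TTP alone while inclusion 1 takes any patient who needs TPE. That comparison has limited force, because inclusion 1 widens the indication openly and no text waives the contraindications.

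A second reply is that *severe* in exclusion 2 was deliberate. It fits other parts of the protocol: the safety scale in section 6.1.3 has a category for reactions that resolve easily, section 4.2 records premedication against allergy, section 7.3.2.6 allows no action on the product, and no rule stops treatment after a mild reaction. This is plausible, but the documents do not state it. If it was the intention, the unqualified list in section 1.3 needs to say so. The reply makes exclusion 2 closer to a trade-off than exclusion 3. It also shows a limit of rewording exclusion 2: that would not settle what to do with a child who reacts mildly at the first TPE and is due for a second.

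A third reply is that exclusion may not help the child. The child would still need TPE, possibly with FFP, and section 1.3 says that pooling lessens allergic reactions compared with single-donor plasma. This stands: a lower risk for the excluded child is not shown.

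**Conclusion.** The point holds as an internal inconsistency in eligibility with a patient-safety bearing. It is clear for IgA deficiency and for past non-severe hypersensitivity, and uncertain for Protein S. Children in these groups *can* meet the entry criteria. How many would do so cannot be derived, because the documents give no prevalence.

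A reader might infer more than the documents support:

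- That contraindicated children will be exposed. The labeling statements and the investigator's judgment may prevent it.
- That the Protein S criterion is wrong to the same degree. Without a definition of *severe*, its gap cannot be sized.
- That a mild past reaction predicts a severe one, or that observed event rates will shift. No text supports either.
- That aligning the criteria would lengthen recruitment by a calculable amount. Any such figure needs an assumed share of excluded candidates for which the documents give no basis.

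The conclusion rests on reading FFP and octaplas as plasma-derived products within exclusion 2, and on treating section 4.1.2 as the sole statement of eligibility. The change is a cheap improvement.

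**What to change.** Amend section 4.1.2 and the synopsis together:

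- **Exclusion 3:** reword to *known IgA deficiency*, dropping the antibody condition.
- **Exclusion 2:** reword to *history of hypersensitivity reaction to FFP, plasma-derived products, octaplas or any excipient*. If children with mild past reactions are to be kept, state and justify that departure from the label in section 4.1.2 and reconcile the list in section 1.3.
- **Exclusion 1:** keep the specific homozygous congenital wording and add *or other known severe deficiency of Protein S*. Replacing the specific criterion with the undefined term alone could create new disagreement between sites.

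Keeping *known* means that no new test or visit is needed.

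The cost is a wording amendment, with IEC/IRB approval under section 10.4 because it bears on patient safety. Some candidates would be lost, in a number that cannot be derived, and they may receive FFP instead. The justified-departure option for exclusion 2 avoids the loss of children with mild past reactions.

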4.2 Prior and Concomitant Therapy

Details of relevant concomitant medications will be recorded in the CRF. Relevant medications are defined as follows:

- Plasma products (e.g., octaplasTM, regular plasma products, etc.) and all other blood products that are administered.
- Antifibrinolytics (ε-aminocaproic acid or tranexamic acid) and any other pharmaceutical pro- or anti-coagulants such as recombinant activated factor VII (rFVIIa), any of the prothrombin complex concentrates, or fibrinogen concentrates.
- Pre-transfusion medications taken to prevent allergic reactions (including steroids)
- An angiotensin-converting-enzyme (ACE) inhibitors (Lisinopril, Captopril, etc.)
- Other medications that the Investigator considers relevant to report for this trial.

Routine medications that are considered standard and/or that have little or no impact on the study data results are not to be entered into the CRF. Relevant concomitant medications or changes thereof must be recorded. If the change influences the patients' eligibility to continue in the trial, the Sponsor must be informed.

4.2.1 Permitted Concomitant Therapy

Concomitant administration of therapies not interfering with the objectives of the study is permitted.

4.2.2 Forbidden Concomitant Therapy

Angiotensin-Converting-Enzyme-inhibitors are forbidden due to the risk of potential hypotensive reactions.

4.3 Withdrawal and Replacement of Patients

4.3.1 Premature Patient Withdrawal

A patient may be withdrawn from the study prior to completion for any of the following reasons:

- Whenever the patient/legal representative(s)/guardian(s) decides it is in the patient's best interest to withdraw
- Whenever the Investigator decides it is in the patient's best interest to be withdrawn
- Pregnancy

For any premature patient withdrawal after study entry, the Investigator will obtain all the required details and document the reason(s) for discontinuation in the CRF. Premature patient withdrawals will be included in the safety analysis.

4.3.2 Patient Replacement Policy

There is no patient replacement policy defined for this protocol. A minimum of 40 patients will be treated in this study.

4.4 Assignment of Patients to Treatment Groups

All patients enrolled in this study will be treated with octaplasTM. The Investigator will inform the Sponsor of new patients enrolled by the submission of patient entry information to the Sponsor.

4.5 Relevant Protocol Deviations

If deviations from the protocol occur, the Investigator should promptly inform the Monitor and the implication of the deviation must be reviewed and discussed. Any deviation must be documented, stating the reason and date, the action taken, and the impact for the patient and/or the trial. The documentation must be kept in the Investigator's Trial File and the Sponsor's Trial File. In case of any major protocol deviation the Investigator and the Sponsor will decide on whether the patient should be withdrawn from this study. Protocol deviations to be considered will include (but not be limited to):

- Violations of the study entry criteria
- Forbidden concomitant medication
- Significant deviations from recommended dose

4.6 Subsequent Therapy

Subsequent treatment will be based on the patient's ongoing clinical response and physician discretion per institutional standard of care.

5 INVESTIGATIONAL MEDICINAL PRODUCT(S)

5.1 Characterization of Investigational Product(s)

The reduced time of S/D treatment within the manufacturing process of octaplas® improved the concentration of plasmin inhibitor and slightly increases that for Protein S compared to its predecessor, octaplas®. The virus safety of octaplas™ was maintained as shown by virus validation studies. With a total inactivation to below the detection limit, the shortened S/D procedure has a time-safety-margin of >98.3% versus >99.5% for the predecessor product.

5.2 Packaging and Labeling

octaplasTM is delivered frozen in sterile, pyrogen-free plastic bags containing 200 mL. The bags are vacuum sealed in a clear plastic wrap and delivered in cartons of 10 units.

Each octaplasTM bag will be labeled as shown below (for blood group A).

NDC 68209-952-01

octaplasTM Pooled Plasma (Human), Solvent/Detergent Treated

For intravenous use only.

Rx only.

200 mL contain 9 - 14 g human plasma proteins, 0.88-1.48 g sodium citrate dihydrate, 0.06-0.24 g sodium dihydrogen phosphate dihydrate, 0.80-1.20 g glycine, ≤ 0.4 mg TNBP and ≤ 1.0 mg Octoxynol. This product contains no preservative.

Store at $\leq -18^{\circ}\text{C}$ (-0.4°F) protected from light. Thawed product should be used immediately and must not be refrozen. Do not use product that is cloudy or has deposits. Unused product must be discarded.

Caution: New Drug--Limited by Federal (or United States) law to investigational use

Exp. Date:

Lot No.:

U.S. License No. 1646

Manufactured by:

Octapharma AB

[name]

[name]

Distributed by:

Octapharma USA Inc.

[name]

[contact]

5.3 Conditions for Storage and Use

The shelf-life of octaplasTM is 36 months when stored at $\leq -18^{\circ}\text{C}$ ($\leq -0.4^{\circ}\text{F}$) and protected from light. After thawing, the product must be used within 24 hours when stored at 1-6°C (33.8°F to 42.8°F) or within 8 hours when stored at room temperature (20 to 25°C or 68°F to 77°F). See package insert in **Appendix 1**.

The Investigator/authorized personnel at the site will ensure that the product is stored in appropriate conditions with restricted access and in compliance with national regulations.

5.4 Dose and Dosing Schedule

octaplasTM, ABO blood group specific, will be given as replacement fluid during TPE and administered per institutional standard of care. It will be used in lieu of FFP during the treatment period.

The total octaplasTM volume infused and time details of each infusion episode will be recorded.

Patients will be followed for one week (7 days) during their therapy which could consist of one or more TPE procedures. The recommended dose is a total plasma volume between 40 to 60 mL/kg, as prescribed by the treating physician. The dosing regimen might differ from the general recommendation, depending on the therapeutic treatment plan and the investigator's evaluation of the respective clinical situation (e.g. plasma exchange). The infusion rate of octaplasTM should not exceed 0.020-0.025 mmol/kg BW (body weight)/min, which is equal to <1 mL/kg BW/min.

5.5 Preparation and Method of Administration

octaplasTM will be used per the approved labeling for the product (see **Appendix 1**). octaplasTM will be administered based on ABO-blood group specificity. In urgent cases, or in circumstances that no same blood group is available (type A octaplasTM for type A recipient), the patient can be administered octaplasTM that is compatible to the recipient's blood group (e.g. type AB octaplasTM can be administered to a type A recipient).

All attempts should be made to ensure adequate octaplasTM blood-type specific inventory is available to meet patient orders. Shipment requests to Octapharma should coincide to meet these needs and should be issued promptly, taking into consideration processing and shipment time.

During the study treatment period, the hierarchy of plasma choice is:

- 1. octaplas™ blood group specific
- 2. octaplasTM blood group compatible
- 3. FFP

Further, if plasma is needed during the TPE follow-up period, octaplasTM should be administered.

5.6 Blinding, Emergency Envelopes and Breaking the Study Blind

Not applicable. This is an open-label study.

5.7 Treatment Compliance

5.7.1 Drug Dispensing and Accountability

octaplasTM will be dispensed per the institutional standard of care, in accordance with the package insert, as prescribed by the treating physician.

5.7.2 Assessment of Treatment Compliance

Having in mind the setting and the fact that study drug administrations will exclusively take place at the investigational site, full compliance is expected.

6 STUDY CONDUCT

6.1 Study Procedures

6.1.1 Screening

The following will take place during Screening:

- Obtaining voluntarily given, written (signed and dated) informed consent by the patient or the patient's legal representative(s)/guardian(s). If children are old enough (age usually deemed by each institution) to understand the risks and benefits of the study, they should also be informed and provide their written assent.
- Review of inclusion and exclusion criteria.
- Perform physical examination.
- Review medical history including current concomitant medication(s), and blood group type (ABO).
- Record demographic data (height, body weight (BW), gender, date of birth, race).
- Blood sample(s)¹ will be drawn for the following safety laboratory parameters: CBC and Chem 7 (refer to **Section** 7.3.5.2 for definition).
- Pregnancy testing for females of childbearing potential will be performed. Confirmation that the subject is not pregnant must be established by a negative pregnancy test result.

6.1.2 1-Week (7-Day) Study Treatment Period

The total treatment period of the study will be a maximum of one week (i.e., 7 days). Within this period, TPE procedures are to be documented.

The following will take place within 24 hours before each TPE:

- Vital signs (heart rate, respiratory rate, temperature, and blood pressure assessment) assessed.
- Blood sample(s) will be drawn for the following safety laboratory parameters: CBC, Chem 7 and ionized calcium (refer to **Section** 7.3.5.2 for definition)².
- If multiple vital signs, and/or laboratory assessments are made before the TPE, the assessment taken most proximal to the start (pre) of the TPE should be recorded in the CRF.

¹ The following blood volume limits for sampling are recommended, if an Investigator decides to deviate from these, this should be justified: NIH Clinical Center Guidelines for Blood Drawn for Research Purposes in the Clinical Center (M95-9) rev 06/05/2009: For pediatric patients, no more than 5 mL/kg may be drawn for research purposes in a single day, and no more than 9.5 mL/kg may be drawn over any eight-week period.

² For the first TPE it is mandatory that, pre– and post–TPE samples for CBC and Chem 7 be tested. If subsequent infusion episodes are performed, pre- and post–TPE samples should be drawn unless considered not medically necessary by the Investigator (e.g., the timing of the pre-TPE sample is close to or overlaps with the timing of the post-TPE sample and it is not necessary to perform, etc.). In the event the pre- or post-TPE laboratory sample(s) are not drawn, the reason for not obtaining the sample(s) will be recorded in the case report form. These CBC and/or Chem 7 parameters may be assessed additionally at any other time point as medically indicated.

The following will take place during each TPE:

- Review and documentation of data regarding any changes in concomitant medications.
- The actual timing and total volume of octaplasTM infused will be recorded.
- Blood sample(s) will be drawn for the following safety laboratory parameter: ionized calcium³
- Any SAEs, ADRs (refer to **Section 7.3.2** for definitions), TEs, TEEs, as well as concomitant medications.
- Record the type of machine used for TPE (filtration or centrifugation).

The following will take place between 30 minutes and 3 hours after each TPE:

- Vital signs (heart rate, respiratory rate, temperature, and blood pressure assessment) assessed.
- Blood sample(s) will be drawn for the following safety laboratory parameters: CBC and Chem 7 (refer to **Section** 7.3.5.2 for definition).
- Any SAEs, ADRs (refer to **Section 7.3.2** for definitions), TEs, TEEs, as well as concomitant medications.

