- 4. Refer to Section 7.3.5.2 for definition of blood test to be done. For the first TPE it is mandatory that, pre—and post—TPE samples for CBC and Chem 7 be tested. If subsequent infusion episodes are performed, pre- and post-TPE samples should be drawn unless considered not medically necessary by the Investigator (e.g., the timing of the pre-TPE sample is close to or overlaps with the timing of the post-TPE sample and it is not necessary to perform, etc.). In the event the pre- or post-TPE laboratory sample(s) are not drawn, the reason for not obtaining the sample(s) will be recorded in the case report form. These CBC and/or Chem 7

- parameters may be assessed additionally at any other time point as medically indicated. If multiple laboratory assessments are made before and after the TPE, the assessment taken most proximal to the start (pre) and after the end of the infusion (post) should be recorded in the CRF.
- 5. For outpatients, follow-up will be done via a telephone interview to assess for any ADRs.
- 6. Confirmation that the subjects of child bearing potential are not pregnant must be established by a negative pregnancy test result obtained during Screening.
- 7. The Investigator's evaluation of overall safety will be performed 24 (+/- 2 hours) hours after each TPE procedure.
- 8. If it is impractical to obtain a blood sample for testing ionized calcium during the follow-up (e.g., an outpatient situation), a post-study treatment sample to test for ionized calcium may be skipped.
- 9. The first sample should be drawn within 90 minutes after start of the TPE.
- 10. The Follow-up procedures (ionized CA and Investigator's Assessment) should be performed 24 hours (+/- 2 hours) after the TPE concludes. The Follow-up procedures may be performed sooner if it is not practical to obtain these during the 24 hour post TPE period. If it is not medically feasible to obtain the Follow-up assessments, the reason must be clearly documented (e.g. patient discharged prior to 24 hours after the end of the last TPE).
- 11. If plasma is needed for administration during the study follow-up period, OctaplasTM should be given. After the end of the follow-up, if plasma is needed, this should be provided according to institutional standard of care.

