6.1.3 Follow-Up

24 (+/- 2 hours) hours after each TPE, the following will be collected:

- Any SAEs, ADRs (refer to **Section** 7.3.2 for definitions), TEs, TEEs, as well as concomitant medications.
- Blood sample(s) will be drawn for ionized calcium levels to assess for citrate toxicity. If it is impractical to obtain a blood sample for testing ionized calcium during the follow-up (e.g. an outpatient situation), this lab assessment may be skipped.

After each TPE the Investigator will provide an overall Assessment of Safety observed for each patient by indicating his or her opinion of one of the following 3 categories best describing the patient's experience with treatment while on study:

- Excellent: defined as the treatment was well tolerated by the patient,
- Moderate: defined as ADR(s) were observed, but easily resolved or not clinically significant,
- Poor: defined as ADR(s) were observed requiring significant medical intervention.

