6.2 Duration of Study

6.2.1 Planned Duration for an Individual Patient

Treatment up to one week (7 days) maximum will be documented. 24 hours (+/- 2 hours) after the last TPE, the final follow-up will be performed to identify and record any SAEs, ADRs, TEs,

³ At least one blood sample should be drawn within 90 minutes after start of each TPE. All subsequent samples should also be reported in the CRF.

TEEs, as well as concomitant medications and Investigator's overall safety assessment. This visit will also be the study completion visit.

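### No required ionized calcium sample is tied to the end of a plasma exchange, so the calcium summary may understate a late fall

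*Protocol*

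**What the plan says.** Ionized calcium is a secondary endpoint (Protocol 3.1.2; SAP 3.2.2). Protocol 6.1.2, 6.1.3 and the flow chart in 3.2.1 set the sampling times:

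- **Before each TPE, within 24 h:** "Blood sample(s) will be drawn for the following safety laboratory parameters: CBC, Chem 7 and ionized calcium" (6.1.2).
- **During each TPE:** "Blood sample(s) will be drawn for the following safety laboratory parameter: ionized calcium" (6.1.2). Footnote 3 to that section sets the timing: "At least one blood sample should be drawn within 90 minutes after start of each TPE". It adds: "All subsequent samples should also be reported in the CRF". Flow-chart footnote 9 has the same 90-minute rule for the first sample.
- **After each TPE:** under "The following will take place between 30 minutes and 3 hours after each TPE", section 6.1.2 lists vital signs, CBC and Chem 7. The flow chart marks these in that column and leaves the calcium cell empty. Chem 7, as defined in 7.3.5.2, has seven analytes and calcium is not one of them.
- **24 h (± 2 h) after each TPE:** "Blood sample(s) will be drawn for ionized calcium levels to assess for citrate toxicity" (6.1.3). This sample may be skipped if impractical, for example in outpatients (6.1.3; flow-chart footnote 8). Footnote 10 adds: "The Follow-up procedures may be performed sooner if it is not practical to obtain these during the 24 hour post TPE period". No earliest time is given.

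SAP 4.1 restates the pre-TPE and 24 h calcium samples and does not mention the in-procedure one. SAP 11.2 tabulates laboratory values and changes from baseline at each time, without defining windows.

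**The concern.** The protocol links citrate toxicity to infusion (1.3; package insert 5.5) and names it among the serious reactions seen with the product. The calcium endpoint exists to show it. Yet the one required in-procedure sample is timed from the start of the TPE, and the next required sample comes about a day after the end. Nothing required looks at the patient when the whole citrate load has just been given, although blood is drawn for other tests between 30 minutes and 3 hours later.

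If calcium falls late in a long TPE, a site that follows the plan exactly may not record the fall. The descriptive calcium summary would then look more reassuring than it should, in a population for which the package insert (8.4) says safety has not been evaluated.

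**Working it through.** The plan states no figure that can be reproduced here: the sample size of 40 is not derived from power, and no citrate clearance is given. The check is the sampling schedule plus simple arithmetic.

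**1. Can a TPE outlast the 90-minute window?** Inputs from Protocol 5.4: 40–60 mL/kg, rate below 1 mL/kg/min. Duration = dose / rate.

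- At 1 mL/kg/min: 40/1 = 40 min to 60/1 = 60 min. This is the shortest case.
- Duration exceeds 90 min when the mean rate is below 40/90 = 0.44 mL/kg/min (40 mL/kg) or 60/90 = 0.67 mL/kg/min (60 mL/kg).
- At an assumed 0.33 mL/kg/min: 40/0.33 = 121 min and 60/0.33 = 182 min. A sample at 90 min precedes the end by 31 or 92 min, with 90 × 0.33/40 = 74% or 90 × 0.33/60 = 50% of the volume given.
- The rule sets only a latest time, so a sample in the first minutes complies in a TPE of any length.

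**2. What can the 24 h sample show?** Assumption: first-order decay of the citrate effect after the end, residual = 2^(−t / half-life). The earliest time inside the window is t = 22 h.

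| Assumed half-life | Left at 22 h | Left at 0.5 h | Left at 3 h |
|---|---|---|---|
| 1 h | <0.001% | 71% | 12.5% |
| 2 h | 0.05% | 84% | 35% |
| 4 h | 2.2% | 92% | 59% |
| 5 h | 4.7% | 93% | 66% |

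For more than 5% to remain at 22 h, the half-life would have to exceed 22 / log2(20) = 5.1 h.

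**3. What can the in-procedure sample show?** Assumption: one compartment and constant infusion over T. The fraction of the end-of-TPE citrate level at time t is (1 − 2^(−t/h)) / (1 − 2^(−T/h)), with half-life h = 0.5–4 h and T = 2–3 h.

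- At 15 min: 10–31%.
- At 45 min: 30–69%.
- At 90 min: 56–93%. By half-life this is 89–93% (0.5 h), 74–86% (1 h), 63–81% (2 h) and 56–78% (4 h).

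**4. Where would an added sample do best?**

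- Fifteen minutes before the end, the same formula gives a lowest value of (1 − 2^(−1.75/4)) / (1 − 2^(−2/4)) = 0.262/0.293 = 89% and a highest of (1 − 2^(−2.75/0.5)) / (1 − 2^(−3/0.5)) = 0.978/0.984 = 99%.
- Thirty minutes after the end, 50% (half-life 0.5 h), 71% (1 h), 84% (2 h) or 92% (4 h) remains. This beats a sample taken at exactly 90 min only at half-lives of about 2 h or more.

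**The case against.** The best reply is that the schedule is consistent on this point and often adequate. Citrate toxicity is expressed in the documents through infusion rate. At rates near the limit a TPE ends within 40–60 minutes, so the in-procedure sample may fall near the end. Even in a 2–3 h TPE, a sample close to 90 minutes sees much of the end level. The wording allows for further in-procedure samples and asks for all of them to be reported. ADRs are recorded continuously, vital signs are taken after each TPE, and clinically significant abnormal results are repeated and followed (7.3.2.2). What is affected is a descriptive secondary summary in a study with no confirmatory testing.

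Most of this stands, and it limits the point. What remains is that none of these features makes a late sample required: a draw at 10 minutes and one the next day comply fully.

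A reader might infer more than the documents support:

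- **That calcium is lowest at the end of the TPE, or that the 24 h sample is too late as a matter of fact.** Both need a TPE duration and a citrate half-life, which the documents do not give. The model is of citrate, not calcium, and it ignores calcium given to counter citrate, which the package insert describes.
- **That an affected child would show two near-normal results.** The 56–93% figure at 90 minutes contradicts this as a general statement. It could happen with an early draw.
- **That early follow-up samples will be pooled into the 24 h time point, or that optional later samples will come mainly from symptomatic children.** SAP 11.2 is silent on windows, and the documents say nothing about who gets extra samples.

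**Conclusion.** The point holds as a cheap improvement, not as an error in the plan. The schedule itself is not in doubt: in the flow chart, 6.1.2, 6.1.3 and 7.3.5.2, no required ionized calcium sample is tied to the end of the TPE, and the existing post-TPE draw omits it. A late fall in calcium could therefore be missed or understated in the laboratory summary.

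The size depends on assumptions. For half-lives of 1–4 h, at most about 2% of an end-of-TPE effect remains at 22 h, so the 24 h value mainly shows recovery. The in-procedure sample may see anything from 10–31% of the end level (at 15 min) to 56–93% (at 90 min) in a 2–3 h TPE. How many TPEs last beyond 90 minutes cannot be told from the documents.

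A reader might also infer that the study would fail to detect citrate toxicity. The documents do not support that: recognized reactions are recorded as ADRs and enter the primary endpoint. The gain is for the laboratory endpoint, that is, for falls in calcium that no one recognizes clinically.

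**What to change.** 1. In the flow chart, Protocol 6.1.2 and 7.3.5.2, and SAP 4.1, add one ionized calcium sample near the end of each TPE. The last 15 minutes of the procedure is preferable, because there the model gives 89–99% of the end level under every assumption used. Otherwise, add the test to the existing post-TPE draw, as close to 30 minutes after the end as practical.
2. Keep the 24 h sample and describe it as a recovery value.
3. In SAP 11.2, use actual sample times relative to the start and end of the TPE. Report follow-up samples taken before 22 h separately from the 24 h time point.
4. While editing 7.3.5.2, reconcile it with 6.1.2 and the flow chart: it ties the pre-TPE calcium sample to the first TPE, whereas they tie it to each TPE.

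The cost is a small extra blood volume per TPE, to be kept within the limits in footnote 1 of Protocol 6.1.1 (5 mL/kg in a day, 9.5 mL/kg in eight weeks), plus short edits to both documents. If the test is attached to the post-TPE draw, no extra needle stick is needed. However, the value is then lost whenever the investigator waives that draw, which the protocol allows after the first TPE.
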